11.4 Reporting Requirements for Specialized AEs

11.4.1 Baseline AEs

Although a pertinent positive finding identified on baseline assessment is not an AE, when possible it is to be documented as “Course Zero” using CTCAE terminology and grade. An expedited AE report is not required if a patient is entered on a protocol with a pre-existing condition (e.g., elevated laboratory value, diarrhea). The baseline AE must be re-assessed throughout the study and reported if it fulfills expedited AE reporting guidelines.

- a. If the pre-existing condition worsens in severity, the investigator must reassess the event to determine if an expedited report is required.
- b. If the AE resolves and then recurs, the investigator must re-assess the event to determine if an expedited report is required.
- c. No modification in grading is to be made to account for abnormalities existing at baseline.

11.4.2 Persistent AEs

A persistent AE is one that extends continuously, without resolution between treatment cycles/courses.

ROUTINE reporting: The AE must be reported only once unless the grade becomes more severe in a subsequent course. If the grade becomes more severe the AE must be reported again with the new grade.

EXPEDITED reporting: The AE must be reported only once unless the grade becomes more severe in the same or a subsequent course.

11.4.3 Recurrent AEs

A recurrent AE is one that occurs and resolves during a cycle/course of therapy and then reoccurs in a later cycle/course.

ROUTINE reporting: An AE that resolves and then recurs during a subsequent cycle/course must be reported by the routine procedures.

EXPEDITED reporting: An AE that resolves and then recurs during a subsequent cycle/course does not require CTEP-AERS reporting unless:

- 1) The grade increases OR
- 2) Hospitalization is associated with the recurring AE.

11.5 Exceptions to Expedited Reporting

11.5.1 Special Situations as Exceptions to Expedited Reporting

An expedited report may not be required for a specific protocol where an AE is listed as expected. The exception or acceptable reporting procedures will be specified in the protocol. The protocol specific guidelines supersede the NCI Adverse Event Reporting Guidelines. These special situations are listed under the CTEP-AERS reporting table for this protocol.

11.6 Reporting Requirements - Investigator Responsibility

Clinical investigators in the treating institutions and ultimately the Study Chair have the primary responsibility for AE identification, documentation, grading, and assignment of attribution to the investigational agent/intervention. It is the responsibility of the treating physician to supply the medical documentation needed to support the expedited AE reports in a timely manner.

Note: All expedited AEs (reported via CTEP-AERS) must also be reported via routine reporting. Routine reporting is accomplished via the Adverse Event (AE) Case Report Form (CRF) within the study database.

11.7 General Instructions for Expedited Reporting via CTEP-AERS

The descriptions and grading scales found in the revised NCI Common Terminology Criteria for Adverse Events (CTCAE) version 5.0 will be utilized for AE reporting and are located on the CTEP website at:

http://ctep.cancer.gov/protocolDevelopment/electronic_applications/ctc.htm.

All appropriate treatment areas should have access to a copy of the CTCAE.

An expedited AE report must be submitted electronically to the NCI via CTEP-AERS at: <https://eapps-ctep.nci.nih.gov/ctepaers>.

- Expedited AE reporting timelines are defined as:
 - **24-Hour; 5 Calendar Days** - The AE must initially be reported via CTEP-AERS within 24 hours of learning of the event, followed by a complete expedited report within 5 calendar days of the initial 24-hour report.
 - **7 Calendar Days** - A complete expedited report on the AE must be submitted within 7 calendar days of the investigator learning of the event.
- Any event that results in a persistent or significant incapacity/substantial disruption of the ability to conduct normal life functions, or a congenital anomaly/birth defect, or is an IME, which based upon the medical judgment of the investigator may jeopardize the patient and require intervention to prevent a serious AE, must be reported via CTEP-AERS **if the event occurs following investigational agent administration.**
- Any death occurring within 30 days of the last dose, regardless of attribution to an agent/intervention under an NCI IND/IDE requires expedited reporting **within 24 hours.**
- Any death occurring greater than 30 days of the last dose with an attribution of possible, probable, or definite to an agent/intervention under an NCI IND/IDE requires expedited reporting **within 24 hours.**

CTEP-AERS Medical Reporting includes the following requirements as part of the report: 1) whether the patient has received at least one dose of an investigational agent on this study; 2) the characteristics of the adverse event including the *grade* (severity), the *relationship to the study therapy* (attribution), and the *prior experience* (expectedness) of the adverse event; 3) the phase (1, 2, or 3) of the trial; and 4) whether or not hospitalization or prolongation of hospitalization was associated with the event.

Any medical documentation supporting an expedited report (e.g., H & P, admission and/or notes, consultations, ECG results, etc.) MUST be faxed within 48-72 hours to the NCI. NOTE: English is required for supporting documentation submitted to the numbers listed below in order for the NCI to meet the regulatory reporting timelines.

Fax or email supporting documentation to COG for **all** IND studies ([contact]; email: [contact]; Attention: COG AERS Coordinator).

- **ALWAYS include the ticket number on all faxed documents.**
- **Use the NCI protocol number and the protocol-specific patient ID provided during trial registration on all reports.**

11.8 Reporting Table for Late Phase 2 and Phase 3 Studies

Expedited Reporting Requirements for Adverse Events that Occur on Studies under an IND/IDE within 30 Days of the Last Administration of the Investigational Agent/Intervention¹

FDA REPORTING REQUIREMENTS FOR SERIOUS ADVERSE EVENTS (21 CFR Part 312)

NOTE: Investigators MUST immediately report to sponsor (NCI) ANY SAEs, whether or not they are considered related to the investigational agent(s)/intervention (21 CFR 312.64).

An AE is considered serious if it results in ANY of the following outcomes:

- 1) Death
- 2) A life-threatening AE
- 3) An AE that results in inpatient hospitalization or prolongation of existing hospitalization for ≥ 24 hours
- 4) A persistent or significant incapacity or substantial disruption of the ability to conduct normal life functions
- 5) A congenital anomaly/birth defect.
- 6) Important Medical Events (IME) that may not result in death, be life threatening, or require hospitalization may be considered serious when, based upon medical judgment, they may jeopardize the patient or subject and may require medical or surgical intervention to prevent one of the outcomes listed in this definition. (FDA, 21 CFR 312.32; ICH E2A and ICH E6).

ALL SAEs that meet the above criteria MUST be immediately reported to the Sponsor via CTEP-AERS within the timeframes detailed in the table below.

| Grade 1-3 Timeframes | Grade 4-5 Timeframes |
|---------------------------------------|---------------------------------------|
| 24-Hour notification, 7 calendar days | 24-Hour notification, 5 calendar days |

NOTE: Protocol-specific exceptions to expedited reporting of SAEs are found in the Specific Protocol Exceptions to Expedited Reporting (SPEER) portion of the CAEPR.

Expedited AE reporting timelines are defined as:

- “24-Hour notification; 5 Calendar Days” - The SAE must initially be reported via CTEP-AERS within 24 hours of learning of the SAE, followed by a complete expedited report within 5 calendar days of the initial 24-hour report.
- “24-Hour notification, 7 Calendar Days” - The SAE must initially be reported via CTEP-AERS

within 24 hours of learning of the SAE, followed by a complete expedited report within 7 calendar days of the initial 24-hour report.

¹SAEs that occur more than 30 days after the last administration of investigational agent/intervention and have an attribution of possible, probable, or definite require reporting as follows:

Expedited 24-Hour notifications are required for all SAEs followed by a complete report

- Within 5 calendar days for Grade 4-5 SAEs
- Within 7 calendar days for Grade 1-3 SAEs

²For studies using nuclear medicine or molecular imaging IND agents (NM, SPECT, or PET), the SAE reporting period is limited to 10 radioactive half-lives, rounded UP to the nearest whole day, after the agent/intervention was last administered. Footnote "1" above applies after this reporting period.

Effective Date: August 30, 2024

11.9 Protocol Specific Additional Instructions and Reporting Exceptions

- **Grades 1 – 4 myelosuppression (anemia, neutropenia, thrombocytopenia, leukopenia, lymphopenia) do not require expedited reporting unless it is associated with hospitalization.**

11.10 Reporting of Adverse Events for commercial agents – CTEP-AERS abbreviated pathway

The following are expedited reporting requirements for adverse events experienced by patients on study who have not received any doses of an investigational agent on this study. Commercial reporting requirements are provided in Table B.

COG requires the CTEP-AERS report to be submitted **within 7 calendar days** of learning of the event.

Table B

Reporting requirements for adverse events experienced by patients on study who have NOT received any doses of an investigational agent on this study.

CTEP-AERS Reporting Requirements for Adverse Events That Occur During Therapy with a Commercial Agent or Within 30 Days¹

| Attribution | Grade 4 | | Grade 5 |
|------------------------------|------------|----------|-----------|
| | Unexpected | Expected | |
| Unrelated or Unlikely | | | CTEP-AERS |
| Possible, Probable, Definite | CTEP-AERS | | CTEP-AERS |

¹This includes all deaths within 30 days of the last dose of treatment with a commercial agent, regardless of attribution. Any death that occurs more than 30 days after the last dose of treatment with a commercial agent that can be attributed (possibly, probably, or definitely) to the agent and is not due to cancer recurrence must be reported via CTEP-AERS.

11.11 Routine Reporting of Adverse Events

Note: The guidelines below are for routine reporting of study specific adverse events on the COG case report forms and do not affect the requirements for CTEP-AERS reporting.

Routine reporting is accomplished via the Adverse Event (AE) Case Report Form (CRF) within the study database. For this study, routine reporting will include all CTEP-AERS reportable events and Grade 3 and higher Adverse Events.

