1.2 Secondary Aims

- 1.2.1 To determine event-free survival (EFS), overall survival (OS), and duration of response (DoR) of children with IFS treated with neoadjuvant larotrectinib prior to local control.
- 1.2.2 To determine the ORR, EFS, OS, and DoR of children with newly diagnosed TRK fusion solid tumors other than IFS treated with neoadjuvant larotrectinib prior to local control.
- 1.2.3 To describe the toxicity of larotrectinib in children with solid tumors and acute leukemia.
- 1.2.4 To determine the percentage of patients with TRK fusion solid tumors with detectable circulating tumor DNA at baseline and after 2 weeks, 4 weeks, 24 weeks of treatment, at the time of discontinuation of larotrectinib therapy, and at progression.

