5.1.1 Non-Hematological Dose-Limiting Toxicity

5.1.1.1 Any Grade 3 or greater non-hematological toxicity with the specific exception of:

- Grade 3 fatigue, nausea, or vomiting of < 3 days duration
- Grade 3 ALT/AST/GGT that return to levels that meet initial eligibility criteria within 7 days of study drug interruption and that do not recur upon re-challenge with study drug. Note: For the purposes of this trial the ULN for ALT is defined as 45 U/L and the ULN for AST as 50 U/L. See [Appendix XII](#) for values that represent thresholds between CTCAE grades.
- Grade 3 or 4 total bilirubin elevation in infants who enrolled with physiologic jaundice and in patients with leukemia. For such patients, only the conjugated (direct) bilirubin will be considered a dose limiting toxicity.
- Grade 3 or 4 fever
- Grade 3 infection < 5 days duration
- Grade 3 weight gain
- Grade 3 hypophosphatemia, hypokalemia, hypocalcemia and/or hypomagnesemia responsive to oral supplementation

5.1.1.2 Any Grade 2 non-hematological toxicity that persists for ≥ 7 days and is considered sufficiently medically significant or sufficiently intolerable by patients that it requires treatment interruption will be considered a dose limiting toxicity.

- Grade 2 allergic reactions that necessitate discontinuation of study drug will not be considered a dose-limiting toxicity.

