9.3 Methods of Analysis

Response criteria are described in [Section 10.2](#). A responder is defined as a patient who achieves a best response (as defined in [Section 10.3.4](#)) of PR or CR on the study. Response rates will be calculated as the percent of evaluable patients who are responders, and confidence intervals will be constructed accounting for the two-stage design.

Toxicity tables will be constructed to summarize the observed incidence by type of toxicity and grade. A patient will be counted only once for a given toxicity for the worst grade of that toxicity reported for that patient. Toxicity information recorded will include the type, severity, time of onset, time of resolution, and the attribution(s) to the study regimen.

Time-to-event analyses (time to progression, progression-free survival, overall survival, and duration of response) will be computed one year after the last enrollment in a stratum. Duration of response will be defined among patients with a confirmed best response of either PR and CR, and will be defined as the time from the first observation of either PR or CR until either the first observation of PD (event) or last known observation of the patient (censored observation).

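### Non-serious Grade 2 dose-limiting toxicities have no required entry on the adverse event form, so the toxicity tables may omit some events that changed treatment

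*Combined protocol and SAP*

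**What the plan says.** **What counts as dose-limiting.** Section 5.1 restricts dose-limiting toxicity (DLT) to events at least possibly attributable to protocol therapy. Most categories start at Grade 3, but Section 5.1.1.2 adds one lower category: non-hematological events of Grade 2 that last a week or more, where the event "is considered sufficiently medically significant or sufficiently intolerable by patients that it requires treatment interruption". One exception is made, for allergic reactions of that grade that lead to discontinuation.

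**What follows from a DLT.** Under Section 5.3 treatment is held. It may resume with a dose reduction if the toxicity resolves within 21 days; otherwise the patient leaves protocol therapy.

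**What goes on the adverse event form.** Section 11.11 sends routine reports to the adverse event form in the study database and says that, for this study, "routine reporting will include all CTEP-AERS reportable events and Grade 3 and higher Adverse Events".

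**What is analysed.** Aim 1.2.3 is: "To describe the toxicity of larotrectinib in children with solid tumors and acute leukemia". Section 9.3 answers it as follows: "Toxicity tables will be constructed to summarize the observed incidence by type of toxicity and grade". It counts each patient once per toxicity, at the worst grade. It also expects the recorded data to include type, severity, onset, resolution and attribution.

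**The concern.** The definition of a dose-limiting event reaches down to Grade 2, but the routine reporting floor is Grade 3. An event can therefore be bad enough to stop the drug and lower the dose without meeting the reporting threshold.

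What is at stake is how complete the safety description is. Treatment can run to 26 cycles, and the median age at enrolment was 8 months (Section 2.7.1). Section 2.7 gives a developmental reason to watch for nervous system effects and describes those reported so far as generally mild. Persistent moderate events that interrupt dosing are informative in that setting. A reader of a table by grade would also not know that its Grade 2 column holds only events that happened to be serious.

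**Working it through.** The documents state no DLT rate, so there is no planned figure to reproduce. The check traces a Grade 2 event that meets Section 5.1.1.2 through each recording route.

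1. **Expedited route.** Section 11.2 makes seriousness, not grade, the trigger. Section 11.8 gives serious Grade 1 to 3 events their own timeframe, and Section 11.6 sends every expedited event to the adverse event form as well. A *serious* Grade 2 DLT is captured.
2. **Routine route.** Apart from expedited events, Section 11.11 names only Grade 3 and higher. A *non-serious* Grade 2 DLT meets neither condition.
3. **General instruction.** Section 10.1 asks for toxicities on the appropriate case report forms and states no grade floor. It does not say which form or which grades. Read as covering all grades, it conflicts with Section 11.11; read as general, it adds nothing.
4. **Dosing records.** The therapy delivery maps ask for held doses and dose modifications under comments. The diaries in Appendix VII ask for missed doses and bothersome effects and are uploaded each cycle (Section 7.1). These leave a trace of the interruption. They do not require an event term, CTCAE grade, attribution, or onset and resolution dates, and nothing links them to the Section 9.3 tables.

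**Other DLT categories.** Section 5.1.1.1 starts at Grade 3. The solid-tumor hematological DLTs in Section 5.1.2 are Grade 3 or 4. The leukemia rule is set by count recovery. Its platelet limit of 20,000/µL lies below the 25,000/µL that the same section gives for Grade 4; the neutrophil grade boundary is not in the documents. The gap is therefore in Section 5.1.1.2.

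**Monitoring rule (Section 9.3.1).** The posterior for the toxicity probability is Beta(0.52 + x, 2.08 + n − x), with a trigger at P(p > 0.20) ≥ 0.70. All 13 tabulated rows reproduce. For example, 2 in 6 gives 0.7001 and 2 in 7 gives 0.632; 14 in 60 gives 0.7135 and 14 in 61 gives 0.691. The rule counts only listed Grade 3 and higher events, which Section 11.11 collects, so it does not change.

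**Size (illustration only).** Expected events without a required entry = N × r × (1 − s). N = 70 is the maximum enrolment in Section 9.1. The per-patient Grade 2 DLT rate r and the serious share s are assumptions.

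| Assumed r | s = 0 | s = 0.5 |
|---|---|---|
| 2% | 70 × 0.02 = 1.4 | 0.7 |
| 5% | 70 × 0.05 = 3.5 | 1.75 |
| 10% | 70 × 0.10 = 7.0 | 3.5 |

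The closest data are the 24 children in the phase 1 study (Section 2.4.1). The one DLT was a Grade 3 ALT elevation, and the one dose reduction described was for Grade 3 neutropenia. If no Grade 2 event led to a reduction there, the one-sided 95% upper limit on the rate is 1 − 0.05^(1/24) = 11.7%. Those data are compatible with none, and they cannot exclude any rate in the table.

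**The case against.** The strongest reply is that collecting Grade 3 and higher events is a deliberate burden decision for a drug at an established dose, approved during the study, and that no planned quantity is damaged. Aim 1.2.3 is descriptive, Section 9 plans no DLT rate, and the only quantitative safety rule is untouched. The case report forms themselves are not in the documents (Section 12.0 says they are posted elsewhere) and may already hold a DLT or dose-modification field. An investigator could also report a Grade 2 DLT as an important medical event under Section 11.2. All of this stands, and it keeps the point small. It does not close the gap: capture would rest on individual judgment or an unseen form, and the rule as written does not require it.

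Three stronger readings are tempting, and the documents do not support them:

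- *Grade 2 DLTs are never recorded.* Serious ones are, and holds leave a trace in maps and diaries.
- *About 4% to 7% of patients have an unrecorded DLT.* That takes the 8 of 55 patients with dose reductions in Section 2.3.2 and assumes that a quarter to a half were for Grade 2 events: 8/55 × 0.25 = 3.6% and 8/55 × 0.5 = 7.3%. No grades are given for those reductions, 43 of the 55 were adults, and the two pediatric phase 1 events were both Grade 3.
- *Affected patients drop out of the toxicity denominator.* A hold longer than 0.15 × 28 = 4.2 days takes a cycle below 85% of full dosing. But Section 9.5 needs 85% in only one cycle, may mean the dose required after a protocol-directed hold, and otherwise admits any possibly related toxicity without a grade floor.

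**Conclusion.** The point holds as a narrow reporting gap. Non-serious Grade 2 events that meet Section 5.1.1.2 are dose-limiting by the protocol's own definition and lead to a hold and a dose reduction, yet they have no required graded entry on the adverse event form. The Section 9.3 tables may therefore leave them out.

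The number left out cannot be computed from the documents. It may be zero; the assumed rates above give between 0.7 and 7.0 events in 70 patients. The conclusion assumes that Section 11.11, as the specific rule, governs what sites enter, and that no unseen form collects these events. A DLT count drawn from the adverse event form could be too low, but the plan promises no such count, so it would be wrong to say that a planned estimate is biased. The response endpoint, the sample size and the monitoring rule do not change.

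**What to change.** 1. Add to the routine reporting sentence in Section 11.11: *and any event meeting the DLT definition in Section 5.1, regardless of grade*.
2. Add a line to Section 10.1 saying that Section 11.11 sets which toxicities go on the adverse event form, so that the two sections agree.
3. In Section 9.3, show Grade 2 DLTs as a separate row, so that the rest of the Grade 2 column is not read as complete.
4. Accrual is complete (Section 2.7.1), so a change to Section 11.11 alone would reach only the remaining treatment cycles. Query the holds and dose reductions already documented in the maps and diaries, and enter any that meet Section 5.1.1.2.

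The cost is a few extra form entries and limited retrospective abstraction. Full Grade 1 and 2 collection is not needed, and no dose or clinical rule changes. If the forms already collect DLTs at any grade, a sentence saying so and linking that field to the tables is enough. If the sponsor prefers not to collect these events, the minimum is to state in Section 9.3 and in the report that the tables cover only Grade 3 and higher and CTEP-AERS reportable events.

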12.0 STUDY REPORTING AND MONITORING

The Case Report Forms and the submission schedule are posted on the COG website with each protocol under “Data Collection/Specimens”. A submission schedule is included.

12.1 CDUS

This study will be monitored by the Clinical Data Update System (CDUS) version 3.0. Cumulative protocol- and patient-specific CDUS data will be submitted quarterly to CTEP by electronic means. Reports are due January 31, April 30, July 31 and October 31. CDUS reporting is not a responsibility of institutions participating in this trial.

12.2 Data and Safety Monitoring Committee

To protect the interests of patients and the scientific integrity for all clinical trial research by the Children's Oncology Group, the COG Data and Safety Monitoring Committee (DSMC) reviews reports of interim analyses of study toxicity and outcomes prepared by the study statistician, in conjunction with the study chair's report. The DSMC may recommend the study be modified or terminated based on these analyses.

Toxicity monitoring is also the responsibility of the study committee and any unexpected frequency of serious events on the trial are to be brought to the attention of the DSMC. The study statistician is responsible for the monitoring of the interim results and is expected to request DSMC review of any protocol issues s/he feels require special review. Any COG member may bring specific study concerns to the attention of the DSMC.

The DSMC approves major study modifications proposed by the study committee prior to implementation (e.g., termination, dropping an arm based on toxicity results or other trials reported, increasing target sample size, etc.). The DSMC determines whether and to whom outcome results may be released prior to the release of study results at the time specified in the protocol document.

